6.1.4 Secondary Outcome Measures

Secondary outcomes will be measured with the adaptive music perception (AMP) test. The test uses an adaptive procedure to find the threshold (Levitt, 1971) of different attributes describing music perception. Based on the recommendations of the AMP test developers (Kirchberger & Russo, 2015; Kirchberger, 2015), only the meter and timbre subscales will be measured. Each subscale is described by three low-level dimensions, i.e. level, pitch, and duration for the meter subscale and brightness, attack, and spectral irregularities for the timbre subscale.

Feedback about their specific music experiences will be evaluated for the general listening program and both music specific listening programs, i.e. reflecting the SP and the IP. The music questionnaire is divided into the overall performance (artifacts, intonation, instrument identification, melody and harmony

recognition), performance of amplification with their own instrument (pleasantness, naturalness, and sound fidelity), and performance of amplification with other instruments. The answer format is based on a visual analogue scale completed with the relevant descriptors anchored at the ends and the middle of the scales (Rutledge, 2009).

The overall benefit given by the hearing aid (IMD) will be evaluated with a general product questionnaire. The questionnaire will focus on the performance of the device with specific questions regarding physical comfort, acoustical feedback, and sound quality.

6.1.5 Safety Objectives

The study aims to assess the overall safety of the IMD by testing for unexpected behaviour from the IMD and by the collection of AEs to identify any new risk factors since their release to the market.

6.1.6 Safety Outcome Measures

The questionnaires used for the secondary outcome will also contain questions to measure the safety of the devices. These questions will specifically address unexpected noise or behaviour from the devices. Unexpected behaviour includes unprovoked feedback or whistling, distorted sounds or artefacts, spontaneous muting or the shutting-off of the device, and any unexplained warning signals, beeps, or loud sounds.

6.2 Analysis method

6.2.1 Preference Test

The preference score is rated on a 5-points Likert scale: SP much better, SP better, no difference, IP better, IP much better. The score distribution is described by the minimum, median, and maximum values and tested with a Wilcoxon signed-rank test with the assumption that ordinal scores from a Likert scale reflect the within subject difference. The null hypothesis is that there is no difference between the tested protocols and the alternative hypothesis is that there is a preference for one of the tested protocols.

Certainty and motivation of preference will be summarized and described separately. The results of this test will be used to answer the 1st and 2nd research questions.

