# 3. BACKGROUND AND RATIONALE

## 3.1 Background and Rationale

The intended use of hearing aids is to amplify sounds to compensate for hearing loss. The initial goal is to amplify speech and facilitate speech understanding especially in noise. Research shows that wireless hearing aids are efficacious for older adults (Humes et al. 2017), and in general, an increase in satisfaction and substantial benefits are characteristic for the wireless hearing aids brought to market during in the last decade.

Music is proven to enhance the lives of older people (Cohen et al., 2002; Lehmberg & Fung, 2010), but many people report a reduction in their ability to enjoy music with a hearing loss (Leek et al., 2008; Creech et al., 2013). Amplification can be used to overcome a hearing impairment and return the joy of music to those with hearing loss. However, for listening to music or particularly, for musicians that play an instrument, the hearing aid settings used for amplifying speech often have adverse effects on music. The common type of compression used to amplify speech, Wide Dynamic Range Compression (WDRC) can lead to poor music quality including distortion, acoustic feedback, and reduced tone quality (Madsen & Moore, 2014). While fast acting WDRC compression is helpful to amplify the soft sounds of speech, for music it disrupts the overall shape of the temporal envelope causing a reduction in the spectral contrast of the music (Madsen et al., 2015). In order to sound natural, the large contrasts between loud and soft sounds of music should not be changed by compression.

Hearing perception abilities are different for normal hearing people compared to hearing-impaired, additionally, musical training (i.e. history of playing an instrument or singing) further alters perception and listening preferences. Normal hearing listeners and those with musical training prefer less compression, meaning less signal processing. While hearing-impaired participants may not strongly favor one condition over the other (Mussoi et al., 2015). For people using hearing aids, music should be treated as a special signal and a program devoted to music listening is recommended (Chasin & Russo, 2004). However, it is not possible to predict in advance the properties of the music signal as it can't be generalized like speech (different instruments, style,

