musical setup). For musicians the dedicated program may require further optimization and fine-tuning specific to their instrument and/or the situations in which they play music.

For this study, Bernafon AG will carry out testing with participants that are musicians with hearing loss to compare dedicated music programs. The current study will compare the standard music program available in the software to one that is fine-tuned for each participant. The Bernafon hearing aids used for the current study are CE- marked and have been on the market for almost one year. The goal is to determine whether musicians will perceive a difference and prefer a fine-tuned music program over the default music program in real-life situations.

The devices used for the trial are the Bernafon Viron 9 miniRITE (MNR) behind-the-ear (BTE) hearing aids. The results of the trial will be used to examine differences in the benefit provided by the two music programs as well as identify further optimization possibilities of the default music program provided by the fitting software. Objective measures will be made with Real Ear Measures (REM) to verify the output of the hearing aids, and subjective differences will be measured with questionnaires and an adaptive music perception test (Kirchberger & Russo, 2015).

All participants are hearing impaired persons that play an instrument. The trial will consist of a total 3 appointments. For the field testing and the lab testing, the order of the programs (optimized or default) will be randomized. It is expected that the optimized program will perform better than the default program for perception and preference testing.

In summary, the primary goal of this study is to evaluate the currently marketed hearing aids regarding their performance with music and to further validate the safety of the devices.

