6.2.2 Adaptive Music Perception (AMP) Test

The AMP test is based on an adaptive procedure that provides the threshold reflecting the amount (time, loudness, pitch...) that each participant can detect above chance. The thresholds are measured on ratio scales: duration in milliseconds, pitch in hertz, loudness in decibels. Kirchberger & Russo (2015) indicate that the thresholds might be influenced by different covariates, like degree of hearing loss or music experience, and by the type of signal processing. Measured thresholds will therefore be modelled by a linear mixed-effect regression with backwards selection based on the variation inflation factor (VIF). This gives a complex picture for the coefficient interpretation as there are 4 test conditions: unaided, aided general program, aided SP, and aided IP. Planned contrasts will be considered:

1. Unaided vs Aided

2. General vs Music-specific programs
3. IP vs SP

The 3rd research question will be answered with a paired t-test on each subscale comparing threshold from the IP to the thresholds from the SP.

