6.2.3 Music Specific Questionnaire

The results from the music questionnaire are scores from a visual analogue scale. The distribution of the scores will be visualized with boxplots for each listening program (General, IP, or SP program) and situation (own musical instrument vs other musical instruments). The effect of listening programs and situation will be evaluated with mixed effect regression model taking into account the hearing loss degree, own instrument category (string, woodwind, or brass), and music experience as fixed effects. Planned contrasts will be considered:

1. General vs Music-specific programs
2. IP vs SP

Results from the second contrast will be used to answer the 3rd research question.

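### The audible-difference question is assigned to a preference test, so a non-significant result leaves it unanswered

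*SAP*

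**What the plan says.** Protocol 11.1 and SAP 2.2 list three research questions. The first is whether the optimized fitting makes an audible difference, the second is whether it is preferred, and the third is whether it improves music perception. Protocol 3.1 also gives the goal in two parts, to "determine whether musicians will perceive a difference and prefer a fine-tuned music program". The null hypothesis in 11.1, however, joins audible difference and preference in one statement.

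The primary item has five categories: SP much better, SP better, no difference, IP better, IP much better (protocol 11.4.2, SAP 6.2.1). On its analysis SAP 6.2.1 says:

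- Description: "The score distribution is described by the minimum, median, and maximum values".
- Test: a Wilcoxon signed-rank test, of which "the alternative hypothesis is that there is a preference for one of the tested protocols".
- Other items: "Certainty and motivation of preference will be summarized and described separately".
- Use: "The results of this test will be used to answer the 1st and 2nd research questions".

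The other comparisons of IP with SP are assigned to question 3. For the adaptive music perception (AMP) test, "The 3rd research question will be answered with a paired t-test on each subscale" (SAP 6.2.2). For the music questionnaire, "Results from the second contrast will be used to answer the 3rd research question" (SAP 6.2.3). No other analysis is assigned to question 1.

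**The concern.** Hearing a difference and preferring one side are separate matters. Two musicians can both hear a clear difference and choose opposite programs. Question 1 has no direction, while the signed-rank test looks only for a net direction. A significant result answers both questions, because a consistent preference between programs whose positions are hidden from the participant implies that they sound different. A non-significant result could mean that most participants reported a difference and split over which program was better, or that few reported one.

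Non-significance is a plausible outcome. Protocol 3.1 notes that "hearing-impaired participants may not strongly favor one condition over the other", although the same paragraph says that musical training shifts preference. The plan does not say what non-significance would mean for question 1. The risk is that the question is left unanswered, or that it is read as a *no* because the null in 11.1 covers both.

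**Working it through.** **Inputs.** n = 18 to 20 (SAP 3.3); two-sided α = 0.05 (SAP 4.1); the five-point item, coded here −2, −1, 0, +1, +2. The documents give no expected split of answers and say that no effect size can be estimated (SAP 3.3), so there is no planned figure to reproduce. The count patterns below are constructed.

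**Test.** Zeros dropped, mid-ranks for ties, exact two-sided sign-permutation p. The plan does not state how zeros are handled; dropping them is my assumption. With m non-zero answers the rank total is m(m+1)/2. If the positive rank sum W⁺ is exactly half of that, p = 1.

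**Two patterns at n=18** (counts in order from SP much better to IP much better):

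- 2/6/2/6/2: m = 16, rank total 16×17/2 = 136. The 12 answers of size 1 have mid-rank 6.5 and the 4 of size 2 have mid-rank 14.5. W⁺ = 6×6.5 + 2×14.5 = 68 = 136/2, so p = 1.00.
- 1/1/14/1/1: m = 4, rank total 4×5/2 = 10. Mid-ranks are 1.5 and 3.5. W⁺ = 1.5 + 3.5 = 5 = 10/2, so p = 1.00.

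Both give minimum −2, median 0, maximum +2. A more extreme pair, 8/0/2/0/8 and 1/0/16/0/1, gives the same four values. The normal approximation with continuity correction also gives p = 1.00 for all four patterns.

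**What separates them.** The share not answering *no difference*, k/n, with Clopper–Pearson limits (lower: 2.5% point of Beta(k, n−k+1); upper: 97.5% point of Beta(k+1, n−k)):

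| Pattern (n=18) | min/median/max | p | Share reporting a difference | Exact 95% CI |
|---|---|---|---|---|
| 2/6/2/6/2 | −2/0/+2 | 1.00 | 16/18 = 89% | 65–99% |
| 1/1/14/1/1 | −2/0/+2 | 1.00 | 4/18 = 22% | 6–48% |
| 8/0/2/0/8 | −2/0/+2 | 1.00 | 16/18 = 89% | 65–99% |
| 1/0/16/0/1 | −2/0/+2 | 1.00 | 2/18 = 11% | 1–35% |

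**All possible results.** The number of ways to place n answers in five categories is C(n+4, 4), which is 7,315 at n=18 and 10,626 at n=20. Those with −2/0/+2 and exact p > 0.05 are:

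- n=18: 1,347 results, with the share reporting a difference from 2/18 to 18/18 (11–100%).
- n=20: 2,059 results, from 2/20 to 20/20 (10–100%).

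These are counts of possible results, not probabilities.

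**How easily non-significance arises.** Suppose every participant reports a difference of equal strength and a share π favours IP (an assumption). The test then reduces to a sign test. It rejects only if at least 14 of 18, or 15 of 20, agree in direction (at π = 0.5 the two-sided rejection probabilities are 0.031 and 0.041).

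| π | P(reject), n=18 | P(reject), n=20 |
|---|---|---|
| 0.5 | 3% | 4% |
| 0.6 | 10% | 13% |
| 0.7 | 33% | 42% |
| 0.8 | 72% | 80% |

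At π = 0.7, with everyone reporting a difference, the result is non-significant in 67% (n=18) or 58% (n=20) of trials.

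**The case against.** The primary objective is preference, and the test is aimed at it. The trial is exploratory, and no text says that non-significance means no audible difference. A minimum of −2 and a maximum of +2 already show that at least one participant on each side reported a difference, and question 1 sets no threshold share. Certainty (a 10-point rating, protocol 5.1) and reasons are also summarized, and the sentence assigning the test to questions 1 and 2 follows directly after them, so they may be meant to count. The proposed share is self-report without a chance-level control. Participants know that two music programs are being compared, and they comment on the sound while IP is tuned, so expectation could raise the share.

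Much of this stands, and it limits the weight of the point. The primary test is not impaired, the harm is one of interpretation, and the remedy describes reported difference rather than proven audibility. It does not remove the gap. The extremes show that someone reported a difference but not how many did. Even if certainty and reasons are included, no rule says how they answer question 1. An exploratory design is a good reason to answer question 1 descriptively, but the plan provides no description that does so.

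**Conclusion.** The concern holds and should be fixed. When the signed-rank test is non-significant, the plan as written cannot answer question 1. With identical planned summaries (−2/0/+2, p > 0.05), the share reporting a difference can lie anywhere from 11% to 100% at n=18, or 10% to 100% at n=20. The point is confined to non-significant results and leaves the preference analysis intact.

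The figures rest on the five-point item with a *no difference* category, as in protocol 11.4.2 and SAP 6.2.1, and on dropping zeros. They say what the summaries can hide, not how likely any pattern is.

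**What to change.** 1. In protocol 11.4.2 and SAP 6.2.1, assign the signed-rank test to question 2 only.
2. In protocol 11.1, separate the preference hypothesis from the audibility question, treat the latter as descriptive, and state that non-significance is not evidence of no audible difference.
3. Report the counts in all five categories.
4. For question 1, report the proportion not answering *no difference* with an exact 95% CI, read alongside certainty and reasons. Note that *no difference* may also mean heard but equally good, and that there is no chance-level control.

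The cost is a few sentences, one table and one proportion, with no new data if the five-point item is used. The limitation is precision: 9/18 gives 26–74% and 10/20 gives 27–73%.

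A side note, on which the point above does not depend: the synopsis, protocol 5.1 and SAP 6.1.2 describe choosing one of the two programs, whereas 11.4.2 and SAP 6.2.1 allow *no difference*. Reconcile these against the questionnaire (protocol Appendix 8, not among the documents reviewed). If the item is a forced choice, it calls for an exact binomial test and cannot answer question 1.

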6.2.2 Adaptive Music Perception (AMP) Test

The AMP test is based on an adaptive procedure that provides the threshold reflecting the amount (time, loudness, pitch...) that each participant can detect above chance. The thresholds are measured on ratio scales: duration in milliseconds, pitch in hertz, loudness in decibels. Kirchberger & Russo (2015) indicate that the thresholds might be influenced by different covariates, like degree of hearing loss or music experience, and by the type of signal processing. Measured thresholds will therefore be modelled by a linear mixed-effect regression with backwards selection based on the variation inflation factor (VIF). This gives a complex picture for the coefficient interpretation as there are 4 test conditions: unaided, aided general program, aided SP, and aided IP. Planned contrasts will be considered:

1. Unaided vs Aided

2. General vs Music-specific programs
3. IP vs SP

The 3rd research question will be answered with a paired t-test on each subscale comparing threshold from the IP to the thresholds from the SP.

6.2.3 Music Specific Questionnaire

The results from the music questionnaire are scores from a visual analogue scale. The distribution of the scores will be visualized with boxplots for each listening program (General, IP, or SP program) and situation (own musical instrument vs other musical instruments). The effect of listening programs and situation will be evaluated with mixed effect regression model taking into account the hearing loss degree, own instrument category (string, woodwind, or brass), and music experience as fixed effects. Planned contrasts will be considered:

1. General vs Music-specific programs
2. IP vs SP

Results from the second contrast will be used to answer the 3rd research question.

6.2.4 General Questionnaire

Reported acoustical feedback: it is asked how often they experience acoustical feedback. Answer possibilities range from never to always on a 5-points Likert scale.

Reported sound quality: rating of the overall sound quality is reported on a 5-points Likert scale, from excellent to very bad.

Results from both questions will be analysed with Wilcoxon signed-rank test to evaluate if the mean rank differs between conditions.

Experienced artifacts, i.e. unexpected sounds or noises must be reported and described individually.

Results from the general questionnaire are used to evaluate the safety of the IMD.

6.3 Missing data

Unless specified otherwise in each objective, no statistical techniques will be used to impute missing data. If a subject's data are missing for any reason, that subject will not be included in that portion of the analysis. The number of subjects included in each analysis will be reported so that the potential impact of missing data can be assessed.

6.4 Harms / Safety Data

The adverse event risks of taking part in the study have been assessed to be low in the study protocol. Numbers of adverse events and serious adverse events will be cross-tabulated for the IMD and categorised by severity. No formal statistical analysis will be conducted, but AEs and SAEs will be closely monitored throughout the process.

[figure not shown]
Serious Adverse Events (SAEs) will be recorded and the site will notify the trial monitor of any SAE, who will then notify the project sponsor within one working day.

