### **4.4 Safety Objectives**

The study aims to assess the overall safety of the IMD by testing for unexpected behaviour from the IMD and by the collection of AEs to identify any new risk factors since their release to the market.

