#### 9.2.3.1 Adverse events

For the recording of adverse events the subjects will be asked for a description of the event including time/date of onset, how long it lasted, how many times it occurred, and if it caused discomfort or pain or a disruption of hearing ability.

Before the end of each appointment, the subjects will be asked if they have experienced any adverse events. It will be explained that adverse events are not restricted to problems related to the hearing aids or their hearing but can include allergies, broken legs, headaches, etc. They will be recorded on the AE forms in the CRF.

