Foreseeable adverse events outlined in the risk management file include discomfort caused by the domes, domes or filters falling off in the ear, no amplification coming from the device causing alarms or traffic to not be heard by the subject, skin reaction if chemical profile of device is changed, maximum output of the device exceeding 132 dB SPL, battery exploding or catching fire, swallowing of a lithium battery, and the device affecting other medical devices worn by the subject. The incidence of all of these risks or adverse events is improbable. To mitigate the risk, the IFU describes how to insert the device, how to change the domes, and how to change a battery in case of no amplification. The IFU describes how to clean the device, domes, and filters in order to not introduce cleaning agents that might change the chemical profile of the hardware of the device. The labelling warns of the potential maximum output of the device. The IFU instructs the user to keep the device away from explosive environments, and to keep them away from children or pets that might swallow the batteries. The IFU warns of interference with implantable devices.

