#### 10.1.1 Foreseeable adverse events and anticipated adverse device effects

No serious adverse events are anticipated. The hearing aid was tested before release to market for safety and has been on the market with no reported problems for almost one year. The following is a list of common and expected adverse device effects.

Headache	Likely	No treatment, self-medication with analgesic, remove device for a period, reduce gain
Sounds are too loud	Likely	Reduce gain, remove device for a period
Tinnitus	Likely	Reduce gain, remove device for a period
Discomfort or pain from device in or around ear	Likely	Remove device and refrain from using for a period, change of dome, change of speaker length
Habituation to the hearing aids and a possible new hearing	Likely	Continued use of hearing aids after the trial is finished.

perception.		
-------------	--	--

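### The only planned adverse event summary cannot separate device-related from unrelated events, although the safety objective is to find new device risks and relatedness is already recorded

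*SAP*

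**What the plan says.** **Objective.** Protocol 4.4 and SAP 6.1.5 share one aim: to assess the safety of the device "by the collection of AEs to identify any new risk factors since their release to the market".

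**Collection.** Protocol 9.2.3.1 has participants told that "adverse events are not restricted to problems related to the hearing aids or their hearing but can include allergies, broken legs, headaches, etc". The AE definition in protocol 10.1.2 likewise covers events whether or not the device caused them.

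**Recording.** Protocol 10.1 requires seriousness and causal relationship to the device or procedure to be documented. The CRF field list in protocol 12.1.1 has entries for adverse device effects (ADE) and serious adverse device effects (SADE) alongside AEs and SAEs.

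**Summary.** SAP 6.4 says: "Numbers of adverse events and serious adverse events will be cross-tabulated for the IMD and categorised by severity". It adds: "No formal statistical analysis will be conducted, but AEs and SAEs will be closely monitored throughout the process". Protocol 11.4.5 says the same.

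**Reference lists.** Protocol 10.1 opens its list of foreseeable events with discomfort caused by the domes and says of the whole list: "The incidence of all of these risks or adverse events is improbable". Protocol 10.1.1, a list of common and expected device effects, includes "Discomfort or pain from device in or around ear" and rates it as likely.

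**The concern.** Finding a new device risk takes two judgements on each event: whether the device plausibly caused it, and whether it was already known. The planned table carries neither. It shows how many events occurred, how many were serious and how severe they were, across everything that happened to the participants in about 20 days of use.

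The study is single-arm (protocol 7.3) and every participant wears the same device, so tabulating for the device adds no comparison from which a device effect could be read. If the report follows the plan as written, its AE table cannot support a statement that new risks were or were not found, although the data needed to do better are collected.

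**Working it through.** The documents give no safety rate or precision target, so there is no figure to reproduce. The check is a comparison of what is recorded with what is reported.

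| Attribute of an event | Recorded? | In the planned summary? |
|---|---|---|
| Seriousness | Yes, protocol 10.1 | Yes, AEs and SAEs counted |
| Severity | Yes, protocol 10.1 | Yes |
| Description of the event | Yes, protocol 9.2.3.1 | No |
| Relation to device or procedure | Yes, protocol 10.1; ADE/SADE entries in 12.1.1 | No |
| Already anticipated | Can be derived from the lists in 10.1 and 10.1.1 | No |

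**What the table can show.** Take two mild, non-serious events: a seasonal allergy and a skin reaction to the device of a kind not seen before. Both are AEs under protocol 10.1.2, and both add one to the same cell. No other margin of the table separates them.

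**Whether another planned source fills the gap.** SAP 6.2.4 has unexpected sounds described individually and uses the general questionnaire for safety. Under protocol 5.2 that questionnaire concerns the general program only and is answered once, after the first field period. Protocol 9.2.3 places the yes/no safety questions in the same questionnaire. Protocol 9.3.3 does mention product questionnaires returned at the last visit, but 9.3.2 hands out only music perception questionnaires for that period. When the two music programs are first worn, AE collection is therefore the main safety source. The music questionnaire rates artefacts on a visual analogue scale (SAP 6.1.4), which does not record AEs.

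**The two lists.** Protocol 10.1 covers discomfort from the domes and gives its incidence as improbable. Protocol 10.1.1 covers discomfort or pain from the device in or around the ear, rates it as likely, and names a change of dome among the responses. The terms are not identical but overlap, and their frequencies conflict.

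**Context only: what 18-20 participants can exclude.** If an event type is seen in 0 of n participants, the one-sided 95% upper bound on its true frequency is 1 - 0.05^(1/n):

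- n = 18: 1 - 0.05^(1/18) = 0.153
- n = 20: 1 - 0.05^(1/20) = 0.139

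This assumes that all 18-20 participants contribute. It depends on n alone and is the same with or without a better table.

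**The case against.** The strongest reply is that the table is not the trial's only route to a new risk. Protocol 10.1 has all AEs and device deficiencies fully investigated, 9.2.3.1 asks for a description of each, 10.1.2 gives a five-level causality scale (headed for SAEs), and 10.1.3 has device deficiencies assessed for their potential to cause an SAE. With 18-20 participants, a new risk would be noticed by reading cases. The study is also exploratory, and the device is CE-marked.

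That stands as far as the raw data go. A reader might infer that the trial cannot identify new risk factors at all; the documents do not support this, because the separating information is recorded event by event. It does not rescue the planned report: SAP 2 sets out to give full details of the methods for the primary report, and no section plans a listing or table that uses this information.

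Three further points:

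- A reader might say that the table sorts by severity alone. It does not: AEs and SAEs are both counted, so seriousness is shown too.
- A reader might infer from the two lists that device discomfort is expected under protocol 10.1.1 and unexpected under 10.1, and that this defeats the table. Both sections treat it as foreseeable, so it is not new under either, and the planned table makes no use of expectedness. The conflict is about frequency only.
- A figure in SAP 6.4 was missing from the copy reviewed and might show more. Protocol 11.4.5 states the same table with no figure, so the gap remains there.

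**Conclusion.** The concern holds for the planned summary. It counts all-cause AEs and SAEs by severity, and so cannot separate device-related from unrelated events or anticipated from new ones, which is what the objective "to identify any new risk factors since their release to the market" requires. This rests on the text of protocol 11.4.5 and SAP 6.4, and on the missing figure in SAP 6.4 not adding a classification that the protocol lacks.

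The consequence is limited: the primary outcome and its test are untouched, and no data are lost. One stated objective lacks a summary that answers it.

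The frequency conflict between protocol 10.1 and 10.1.1 is a separate, smaller defect. The documents do not settle which wording is right, and the passages must be reconciled.

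The 15.3% to 13.9% bound does not measure this defect. It only reminds the reader that an event type not seen in 18-20 participants could still be fairly common.

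**What to change.** 1. In protocol 11.4.5 and SAP 6.4, report numbers of events and of participants by event term, by device-relatedness (ADE/SADE versus not related) and by whether the event is on the anticipated list, with severity within these. At 18-20 participants a line listing with these columns would suffice.
2. Reconcile the frequency wording for device discomfort in protocol 10.1 and 10.1.1 before either serves as the anticipated list, and name that one list in the SAP.
3. Optionally, print the zero-event bound (15.3% at 18 participants, 13.9% at 20) beside any statement that no new risk was seen.

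The cost is a table or listing shell and a few sentences in each document. No new data collection is needed, because relatedness and the event description are already recorded.
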